Although the protocol mentioned analysis of the symptom duration through Day 28, daily symptom level assessment ceases on *DayA15*. Therefore, the *DayA28* symptom assessments will be ignored when determining symptom duration.

- EQ-5D-5L measures (administered at baseline, 28 days, and 6 months)[1, 2]
 - Visual Analog Scale: 0 to 100 scale. If the value is missing because the individual is known to be deceased when the assessment was to have occurred, the VAS change since baseline will be post-processed to -101 (i.e., worse than possible for any survivor) after multiple imputation (see Section 7.4.5).
 - Index measure: The index measure will use coefficients from the cTTO Model (Model 1 in Table 2 of [2]) to provide a univariable summary of the five component dimensions. If the value is missing because the individual is known to be deceased when the assessment was to have occurred, the index measure will be set to 0. Otherwise, if any of the five dimensions are missing, the index measure will be regarded as missing.
- PCL-5 Total (baseline, 28 days, and 6 months): The 20 items are scored as 0–4 each, producing a total from 0–80.[3] The cited reference does not provide specific guidance on what percentage of missing values may be imputed with the mean of the corresponding non-missing values. In the absence of such a recommendation, if no more than 4 (i.e., 20%) of the relevant items are missing for an individual's total, then the average of the individual's observed item scores from the total will be substituted for the missing items to impute the total. If more than 4 items are missing, the total will be regarded as missing. In addition, subtotals of potential interest may be considered: cluster B (items 1–5), cluster C (6–7), cluster D (8–14), and cluster E (15–20); see [3]. Up to 20% of missing values within a cluster would be imputed with the average of the observed scores in the cluster for determining these subtotals. If the value is missing because the individual is known to be deceased when the assessment was to have occurred, the PCL-5 change since baseline will be post-processed as 81 (i.e., worse than possible for any survivor) after multiple imputation; similar adjustments will be made for cluster subtotals.
- GAD 7 Total (baseline, 28 days, and 6 months): The 7 items are scored as 0–3 each, producing a total from 0–21.[4] The cited reference does not provide specific guidance

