7.4.5 Quality of life (EQ-5D-5L Assessment)

The EQ-5D-5L quality of life assessment is administered at baseline, 28 days, and 6 months and we will analyze the VAS and an index measure, as described in Section 5.4. Multiple imputation of missing values will be implemented prior to analysis to improve inference given the expectation that missingness may depend on other characteristics. Imputation will include a death indicator for subjects who were known to have died before the assessment was to have occurred. After imputation, differences between day 28 (6 months) and baseline values of the VAS will be calculated. Any subjects whose measurement at day 28 (6 months) is missing because the individual died will then be post-processed to have a value worse than the worst possible difference among survivors (i.e., -101). Mean differences between day 28 (month 6) values and baseline will be compared between arms using a suitable approach (e.g., Van Elteren test), while adjusting for age stratum.

A similar analytical approach will be taken for the EQ-5D-5L index measure, except that the index measure will be set to 0 for individuals who were missing the assessment because they were deceased. No other missing index measure values will be imputed. Note that survivors may have a lower value for this index measure (i.e., <0) than those who are deceased.

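### The EQ-5D-5L index is the only patient-reported score in SAP 7.4.5 to 7.4.8 left unimputed, so survivors with missing values drop out while known deaths with a baseline stay in at level 0

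*SAP*

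**What the plan says.** SAP 2.1.4 lists the EQ-5D-5L VAS and index, PHQ-9, GAD-7 and PCL-5 as exploratory outcomes at baseline, 28 days and 6 months.

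SAP 7.4.5 opens with a general rule for the EQ-5D-5L: "Multiple imputation of missing values will be implemented prior to analysis to improve inference given the expectation that missingness may depend on other characteristics". Sections 7.4.6 to 7.4.8 apply the VAS method to PHQ-9, GAD-7 and PCL-5. For the index, 7.4.5 refers to a similar approach but makes two exceptions. The first concerns deaths: "except that the index measure will be set to 0 for individuals who were missing the assessment because they were deceased". The second concerns everyone else: "No other missing index measure values will be imputed". No reason is given for the second.

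SAP 5.4 defines when the index is missing: "Otherwise, if any of the five dimensions are missing, the index measure will be regarded as missing". It handles deaths differently on the VAS: "the VAS change since baseline will be post-processed to -101 (i.e., worse than possible for any survivor) after multiple imputation". PCL-5, GAD-7 and PHQ-9 have matching rules for deaths.

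On the ordering of deaths and survivors on the index, 7.4.5 is open: "Note that survivors may have a lower value for this index measure".

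**The concern.** The reason given for imputing is that people with missing forms may differ from those without. That reason applies equally to the VAS and the index, which come from one form at one visit. With the VAS imputed and the index analysed on complete cases, the two can disagree through handling alone.

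The exempted score also has the strictest missing-item rule. One missing dimension out of five loses the index. By contrast, PCL-5 tolerates 4 missing items of 20, PHQ-9 tolerates 2 of 9 and GAD-7 tolerates 1 of 7, and all three totals are then multiply imputed as well.

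Missing six-month forms are foreseeable. Protocol 5.5 allows a missed six-month survey to be collected for up to a year after that timepoint, whereas SAP 5.4 analyses only those from 2 weeks before to 2 months after. Forms later than that become missing values, which are imputed for the VAS and dropped for the index.

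At stake are precision, possible complete-case bias, and an imbalance in who remains: a death supplies its own follow-up value, while a survivor who does not return a complete form supplies none.

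**Working it through.** **1. Rules side by side (SAP 5.4, 7.4.5 to 7.4.8)**

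| Score | Missing values in survivors | Value for a death |
|---|---|---|
| VAS | multiply imputed | change = -101 |
| PCL-5 | multiply imputed | change = 81 |
| GAD-7 | multiply imputed | change = 22 |
| PHQ-9 | multiply imputed | change = 28 |
| EQ-5D-5L index | not imputed | level = 0 |

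The first four death codes reproduce as the worst possible survivor change plus one unit in the bad direction: -100 - 1 = -101; 80 + 1 = 81; 21 + 1 = 22; 27 + 1 = 28. The index differs in both columns.

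**2. What a death contributes on the index.** The zero is a level, and the comparison is of change from baseline. Change for a death = 0 - baseline. With baseline 0.80, for example, the change is -0.80. A death with no baseline index has no change score and also drops out, because baseline values are not imputed either.

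**3. Share of deaths in the analysed set.** Let N be the arm size, d the deaths (all with a baseline index) and m the fraction of survivors with a missing follow-up index.

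- Share with survivors imputed: d/N
- Share under the SAP rule: d / [d + (N - d)(1 - m)]
- Ratio, for small d: about 1/(1 - m)

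N = 200 per arm is from Protocol 2.7. The documents give neither d nor m, so both are assumed here. With d = 2:

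| m (assumed) | Calculation | Share of deaths | Ratio to d/N |
|---|---|---|---|
| 0% | 2/200 | 1.00% | 1.00 |
| 10% | 2/(2 + 178.2) | 1.11% | 1.11 |
| 20% | 2/(2 + 158.4) | 1.25% | 1.25 |
| 30% | 2/(2 + 138.6) | 1.42% | 1.42 |
| 40% | 2/(2 + 118.8) | 1.66% | 1.66 |

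For d from 1 to 8 the ratio is about 1.11 at m = 10% and runs from 1.66 down to 1.62 at m = 40%. If deaths and survivors lack a baseline at the same rate, that rate cancels. The ratio comes from follow-up missingness alone.

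**4. Effect on an arm mean (all values assumed).** Take 2 deaths in 200, baseline 0.85 in the deaths and a change of +0.05 in survivors.

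- m = 0: (2 × -0.85 + 198 × 0.05)/200 = 8.2/200 = 0.0410
- m = 30%: (2 × -0.85 + 138.6 × 0.05)/140.6 = 5.23/140.6 = 0.0372

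The shift is 0.0038 within one arm. It matters for the comparison only to the extent that it differs between arms.

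**The case against.** The strongest defence is that this is an exploratory outcome with probably few deaths, and that death at 0 on a utility index is a deliberate, stated choice. Complete-case analysis also biases the arm comparison only if missingness is related to outcome differently by arm, or in ways that the age-stratum adjustment does not absorb, and the documents do not show that it is. All of this stands, and it limits the size of the point. It does not explain why the section's own reason for imputing stops at the index.

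A reader might infer stronger points that the documents do not support:

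- *That deaths receive a change score of 0, meaning no change.* They do not. SAP 5.4 says "the index measure will be set to 0", which is the level.
- *That a fixed, sizeable fraction of survivors is lost.* The documents give no return rate. At m = 0 there is no over-weighting.
- *That every death is retained.* Only deaths with a baseline index are.
- *That ranking a death above a survivor is an error.* It can happen: a death from 0.40 (change -0.40) ranks above a survivor going from 0.95 to 0.50 (change -0.45), even though that survivor's index is positive. The caveat in 7.4.5 speaks only of survivors below 0, so it does not cover this case. Still, valuing death at 0 rather than ranking it worst is a choice of estimand and is disclosed. The Van Elteren test is also named only as an example, and if means were compared an extreme death code would itself drive the result.

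**Conclusion.** The point holds as an inconsistency that is cheap to remove. One of five patient-reported scores is left on complete cases, against the rationale stated in the same section and without explanation. Survivors with incomplete data leave the analysis, while known deaths with a baseline index stay in at level 0. The share of deaths is inflated by about 1/(1 - m): nil at 0% missing, 1.11-fold at 10% and 1.66-fold at 40%. Those values of m are assumptions, as is the number of deaths. In the illustration the arm mean moves by less than 0.004.

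The loss of survivors' data does not depend on the number of deaths and is the main reason to change the rule. No bias in the treatment comparison has been shown, and no primary or secondary conclusion is affected.

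**What to change.** In SAP 7.4.5, replace the sentence "No other missing index measure values will be imputed" with a rule to this effect:

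1. Missing index values (baseline, and follow-up in survivors) are multiply imputed in the same imputation as the VAS.
2. After imputation, the index level is set to 0 for participants known to have died before the assessment.
3. Change from baseline is computed after that step.

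If the sponsor prefers to keep the index unimputed, the SAP should give the reason.

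Timing needs care. The SAP change log for version 1.4 places that round of decisions after the primary manuscript was drafted and refers to results already seen. It does not say whether index results were among them. If the change is made after results were viewed, it should be labelled post hoc, as SAP 1.2 requires for unplanned analyses, with the complete-case result reported beside it.

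An analysis ranking deaths worst may be added as an optional sensitivity analysis; it is not a correction.

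The cost is a few sentences and one more measure in an imputation already planned. The downside is slightly more analysis work, for a gain confined to an exploratory outcome.

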7.4.6 Six-month depression (PHQ-9 Total)

Analysis of the PHQ-9 Total will be conducted in the manner analogous to that of the 28-day and six-month EQ-5D-5L VAS.

7.4.7 Six-month anxiety (GAD-7 Total)

Analysis of the GAD-7 Total will be conducted in the manner analogous to that of the 28-day and six-month EQ-5D-5L VAS.

7.4.8 Post-traumatic stress disorder (PCL-5 Total)

Analysis of the PCL-5 Total will be conducted in the manner analogous to that of the 28-day and six-month EQ-5D-5L VAS.

7.4.9 Additional Analyses for Time-to-event Outcomes

Kaplan-Meier incidence curves will also be created by treatment group for the following:

- Time to death
- Time to first hospitalization and death out of the hospital (as competing risks)
- Time to no symptoms and death (as competing risks)

For all but the first, the cumulative incidence curves for the composite outcome including death would be depicted along with cumulative incidence curves for death and for the other outcome overlaid on the plot.

7.5 Safety Analyses

7.5.1 Formal Safety Outcome(s)

In addition to outcomes described earlier in this section, additional exploratory safety outcomes for this trial include:

- Mortality by 14 days
- Mortality by 28 days
- Hospital admission by 28 days

The analysis of each of these additional safety outcomes will be conducted in analogous fashion to the six-month mortality and six-month hospitalization endpoints (see Sections 7.4.2 and 7.4.3). For these exploratory outcomes, the analysis will be conducted on the ITT and SAFETY populations, with emphasis on the former.

7.5.2 Adverse Events

Per the protocol, AEs will be recorded through the earlier of hospitalization and Day 14.

Collected adverse events The protocol identifies adverse events (AEs) to be collected in AE report forms of the database. These include

- Serious adverse events (SAEs)
- Non-serious AEs judged by investigator as related to study drug or study procedures or of uncertain relationship
- AEs resulting in permanent discontinuation of study drug

Summaries Formal statistical analysis of adverse events is not planned, other than what has been noted previously in this SAP for adverse events that are used to define trial outcomes. However, descriptive summaries of adverse events will be created to assist the DSMB in monitoring safety.

For the closed session of DSMB meetings the overall number and percentage of patients with AEs and SAEs will be summarized, overall and by Medical Dictionary for Regulatory

Activities (MedDRA) coding. AEs will be classified by relatedness, expectedness, seriousness, intensity, action taken, outcome, and modification to study treatment. AEs will be summarized by seriousness, relatedness, and expectedness, and SAEs will be summarized by relatedness and expectedness. This will be done by treatment arm for the SAFETY population (principal focus) and for the ITT population. Generic treatment designations are preferred for interim DSMB meetings unless the DSMB requests otherwise.

